6.3.6 IV Infusion and Infusion Set Details

Blinatumomab must be administered through a central line at rate of 5 mL/hr IV over 24 hours through an acceptable IV line. Only **PVC non-DEHP lines with a 0.2 µm inline filter are acceptable**. Do not flush the IV line as it will create an IV bolus to be administered into the patient. For outpatient administration, use FDA approved pumps. Only the exact volume should be administered; any remaining overfill should be discarded appropriately.

6.3.7 Infusion Pump Requirements

Use a programmable pump that is approved by the appropriate regulatory authority for the country in which the subject is undergoing treatment. The pump alarm must be visual and auditory. The pump must be lockable. **Elastomeric pumps are NOT allowed.** CADD pumps are allowed; however, the cassettes used in CADD pumps are not compatible with blinatumomab and thus, **not** allowed.

Record all infusion interruptions. Technical or logistical interruption must be as minimal as possible and re-start the infusion as soon as possible. If an interruption is longer than four hours, the re-start of the infusion must take place in the hospital under supervision of the investigator. Monitor patients for potential adverse events as described in the protocol and the Investigator Brochure.

Monitor patients for cytokine release syndrome, tumor lysis syndrome, and infusion reaction. Refer to protocol for specific recommendation. Monitor patients for psychiatric events such as confusion, disorientation, and cognitive attention disturbances. Patients should not drive or operate dangerous machinery while receiving blinatumomab.

Risk of Serious Adverse Reactions in Pediatric Patients Due to Benzyl Alcohol Preservative: Serious and fatal adverse reactions including “gasping syndrome” can occur in neonates and infants treated with benzyl alcohol-preserved drugs, including BLINCYTO (with preservative). The “gasping syndrome” is characterized by central nervous system depression, metabolic acidosis, and gasping respirations.

When prescribing BLINCYTO (with preservative) for pediatric patients, consider the combined daily metabolic load of benzyl alcohol from all sources including BLINCYTO (with preservative) (contains 7.4 mg of benzyl alcohol per mL) and other drugs containing benzyl alcohol. The minimum amount of benzyl alcohol at which serious adverse reactions may occur is not known.

Due to the addition of bacteriostatic saline, 7-day infusion bags of Blinatumomab solution contain benzyl alcohol and are not recommended for use in any patients weighing less than 22 kg. Prepare Blinatumomab solution for infusion with preservative-free saline in 24-hour or 48-hour infusion bags for patients weighing less than 22 kg. Please refer to Appendix 2 for infusion instructions for patients weighing less than 22 kg.

6.3.8 Supplier

Blinatumomab and the solution stabilizer for blinatumomab is supplied by Amgen, Inc. and will be distributed by Amgen to Children's Hospital of Wisconsin and American Family Children's Hospital/University of Wisconsin. Do not use commercial supply.

6.3.9 Obtaining the Agent

6.3.9.1 Agent Ordering

Amgen supplied agent may be requested by the eligible participating investigator (or their authorized designee) at each participating institution (Children's Hospital of Wisconsin and American Family Children's Hospital/University of Wisconsin).

To request shipment for this order: [contact] or Fax orders to [contact]
 ATTN: Amgen GCSCM CDCs

Order:	 Initial  Resupply  Rush (shipment within 72 hours of receipt) Provide Justification:	
Study Title:		
Study Sponsor:		
Sponsor Study #:	Amgen Reference #:	
Product Description		
Blinatumomab (AMG 103)		
Quantity Requested		
Blinatumomab (AMG 103)	38.5 µg/vial; 15 vials per box	vials/ boxes
IV Solution Stabilizer for Blinatumomab (AMG 103)	10 mL vial; 6 vials per box	vials/ boxes
Site Comments		
Investigator:	Date of Request:	
Amgen Site#:	Preferred Arrival Date:	

Shipments are processed on Monday through Thursday 12:00 p.m. PST. ***Drug Shipment***

Requests received on Thursday after 12:00 p.m. PST will be shipped on the following Monday.

6.4 Supportive Care Guidelines

All supportive measures consistent with optimal patient care will be given throughout the study.

6.4.1 Venous Access

A central venous access device, preferably a double lumen, is strongly recommended for this study.

Anti-emetics will be used according to standard medical practice. Growth factor use is allowed on this study.

6.4.2 Antimicrobial Prophylaxis

Patients should be placed on standard of care prophylaxis during this time period at the discretion of the treating physician according to institutional guidelines for PCP, HSV, bacterial and fungus.

6.5 Follow-Up Period

All subjects, including those who discontinue protocol therapy early, will be followed for 30 days after the last dose of blinatumomab or until the start of the transplant preparative regimen (or other therapy), whichever occurs earlier.

Subjects removed from the study treatment for unacceptable SAEs will be followed until resolution or stabilization of the adverse event. SAEs will be followed until completion.

7.0 DOSING DELAYS/DOSE MODIFICATIONS

The most frequent serious adverse events noted in patients treated with blinatumomab to date are disorders of the nervous system, both peripheral and central, and systemic cytokine release syndrome (CRS). Both categories of events are more likely to occur within the first week of treatment with blinatumomab, and both categories of events are usually reversible and able to be managed with attentive supportive care.

AEs related to blinatumomab that require treatment interruption (according to table below) and do not resolve to CTCAE (Version 5.0) \leq Grade 1 within 14 days will require permanent discontinuation of blinatumomab treatment. If the patient is eligible to continue protocol therapy (e.g. HCT), then the patient may, at the discretion of the investigator and family, continue to receive protocol therapy. Otherwise, the patient will be off protocol therapy.

In the case that the AE(s) **DO resolve within 14 days**, blinatumomab treatment may resume at a **reduced dose of 5 mcg/m²/day** to complete the 28-day course (not counting the duration of treatment interruption).

NOTE: For Grade 4 Nervous System/Psychiatric, Grade 3 or 4 Central Nervous System: Seizure and Grade 4 thromboembolic AEs, blinatumomab must be permanently discontinued.

For patients who had experienced a \geq Grade 2 Neurologic Systems and Psychiatric AE related to blinatumomab, **no dose escalation beyond 5 mcg/m²/day will be permitted** for subsequent cycles. For patients who experienced other AEs related to blinatumomab, subsequent cycles will begin at the reduced dose of 5 mcg/m²/day but **may escalate to 15 mcg/m²/day** after 7 days if there are no significant blinatumomab-related AEs.

A **second AE** that requires interruption **will require permanent discontinuation** of treatment and the patient will be off protocol therapy.

The resumption of the infusion at the reduced dose should be accompanied by **dexamethasone premedication** as indicated in the relevant subsection of Section 4.0, should be performed in the hospital under supervision of the investigator and patients should be observed for at least 72 hours after the start of the next infusion before considering discharge to the outpatient setting.

Table 1: Dose Modifications for Adverse Events (AE) Occurring During Blinatumomab Administration

Category: AE (CTCAE v5.0)	AE Grade	Patients Greater Than or Equal to 45 kg	Patients Less Than 45 kg
Cytokine Release Syndrome (CRS)	3	Withhold blinatumomab until resolved, then restart blinatumomab at 9 mcg/day. Escalate to 28 mcg/day after 7 days if the toxicity does not recur.	Withhold blinatumomab until resolved, then restart blinatumomab at 5 mcg/m ² /day. Escalate to 15 mcg/m ² /day after 7 days if the toxicity does not recur.
	4	Discontinue blinatumomab permanently	
Neurologic Toxicity	Seizure	Discontinue blinatumomab permanently if more than one seizure occurs.	
	3	Withhold blinatumomab until no more than Grade 1 (mild) and for at least 3 days, then restart blinatumomab at 9 mcg/day. Escalate to 28 mcg/day after 7 days if the toxicity does not recur. If the toxicity occurred at 9 mcg/day, or if the toxicity takes more than 7 days to resolve, discontinue blinatumomab permanently.	Withhold blinatumomab until no more than Grade 1 (mild) and for at least 3 days, then restart blinatumomab at 5 mcg/m ² /day. Escalate to 15 mcg/m ² /day after 7 days if the toxicity does not recur. If the toxicity occurred at 5 mcg/m ² /day, or if the toxicity takes more than 7 days to resolve, discontinue blinatumomab permanently.
	4	Discontinue blinatumomab permanently	
Other Clinically Relevant Adverse Reactions	3	Withhold blinatumomab until no more than Grade 1 (mild), then restart blinatumomab at 9 mcg/day. Escalate to 28 mcg/day after 7 days if the toxicity does not recur. If the toxicity takes more than 14 days to resolve, discontinue blinatumomab permanently.	Withhold blinatumomab until no more than Grade 1 (mild), then restart blinatumomab at 5 mcg/m ² /day. Escalate to 15 mcg/m ² /day after 7 days if the toxicity does not recur. If the toxicity takes more than 14 days to resolve, discontinue blinatumomab permanently.
	4	Considering discontinuing blinatumomab permanently	

Table Footnotes

1. Grading of cytokine release syndrome (CRS) severity should be performed according to that of

Lee et al (see below table). As many of the symptoms of CRS overlap with those of other medical complications such as infection, attribution should be carefully considered. Accurate application of this grading system requires clinical judgment to confirm that the symptoms are most likely due to CRS rather than to another medical condition. In all grades of CRS, aggressive supportive care is required. In Grade 2 or 3 CRS, careful monitoring of cardiac function is strongly suggested.

Grade 1	Symptoms are not life threatening and require symptomatic treatment only, e.g. fever, nausea, fatigue, headache
Grade 2	Symptoms require and respond to moderate intervention Oxygen requirement < 40%, or Hypotension responsive to fluids or low dose of one vasopressor, or Grade 2 organ toxicity
Grade 3	Symptoms require and respond to aggressive intervention Oxygen requirement >= 40%, or Hypotension requiring high dose of one vasopressor or multiple vasopressors, or Grade 3 organ toxicity or grade 4 transaminitis
Grade 4	Life-threatening symptoms Requirement for ventilator support, or Grade 4 organ toxicity (excluding transaminitis)

2. In patients with ALL receiving BLINCYTO in clinical studies, neurological toxicities have occurred in approximately 65% of patients. Among patients that experienced a neurologic event, the median time to the first event was within the first 2 weeks of BLINCYTO treatment and the majority of events resolved. The most common ($\geq 10\%$) manifestations of neurological toxicity were headache, and tremor; the neurological toxicity profile varied by age group. Grade 3 or higher (severe, life-threatening, or fatal) neurological toxicities following initiation of BLINCYTO administration occurred in approximately 13% of patients and included encephalopathy, convulsions, speech disorders, disturbances in consciousness, confusion and disorientation, and coordination and balance disorders. Manifestations of neurological toxicity included cranial nerve disorders. The majority of neurologic events resolved following interruption of BLINCYTO, but some resulted in treatment discontinuation. There is limited experience with BLINCYTO in patients with active ALL in the central nervous system (CNS) or a history of neurologic events. Patients with a history or presence of clinically relevant CNS pathology were excluded from clinical studies.

Monitor patients receiving BLINCYTO for signs and symptoms of neurological toxicities. Advise outpatients on BLINCYTO to contact their healthcare professional if they develop signs or symptoms of neurological toxicities. Interrupt or discontinue BLINCYTO as recommended in Table 1 above.

Of note, most AEs in the psychiatric disorder category are unlikely to be caused by blinatumomab and generally require supportive care rather than dose modification or discontinuation of blinatumomab (e.g., Insomnia, Depression, Anxiety). Psychiatric AEs that may reflect underlying central nervous system toxicity (e.g., Confusion, Delirium, Hallucinations, Psychosis) are of

greater interest, particularly if accompanied by other AEs in the nervous system disorders category" follow the recommendations from the USPI.

3. In the first days of treatment, transient DIC-like pictures may develop. Because patients are at risk for capillary leak syndrome and cytokine release syndrome, appropriate supportive care with dexamethasone (described above), blood products and factors (packed red cells, platelets, cryoprecipitate, fresh frozen plasma), vitamin K, and/or albumin should be considered according to institutional standards of care. Particularly in the first week of infusion, when the risk of capillary leak and cytokine release is more prominent, appropriate use of blood products and factors is preferred if laboratory indications suggest the need for replacement, as large volumes of crystalloid fluids tend to exacerbate the capillary leak.
4. In the first days of treatment, a rapid transient drop in platelets, neutrophils and/or hemoglobin may be observed. These effects are not necessarily cytokine-mediated. Counts typically recover to baseline during treatment, and usually within two weeks of starting blinatumomab. Transfusion of blood and platelets should be performed according to appropriate institutional standards.
5. In the first days of treatment, transient increases in transaminases up to over 1000 U/L may develop. These have generally returned to baseline in the 1st week of treatment.
6. Decrease in serum immunoglobulins have been observed in patients treated with blinatumomab. Intravenous immunoglobulin should be administered according to institutional standards but is recommended for any patient with a total IgG level below 400. Immunoglobulin must not be administered through the line through which blinatumomab is actively being infused.

* Definitions of supportive care abbreviations:

DEX: Dexamethasone should be administered at a total daily dose of at least 0.2 - 0.4 mg/kg/day (maximum 24 mg per day) administered preferably intravenous divided 3 - 4 times daily for at least 1 day but no more than 4 days. The dose should then be stopped or tapered as clinically indicated.

SZ: Appropriate imaging should be performed to evaluate for possible hemorrhage or thrombosis, and other diagnostic procedures should be performed as clinically appropriate. Prophylactic anticonvulsant treatment with a therapeutic dose of institutional standard agents (e.g., lorazepam, phenytoin, levetiracetam) should be administered if seizures develop, and continued throughout the blinatumomab infusion. Anti-convulsant therapy should be considered starting at least 24 - 48 hours prior to any subsequent blinatumomab infusions and continuing for the remainder of those treatment cycles. Diagnostic measures to exclude potential infectious causes should be conducted once the patient has stabilized (i.e., a lumbar puncture to evaluate for bacterial, viral or fungal sources should be performed). Any identified pathology should be treated as clinically appropriate.

CNS: A daily finger-nose-finger or writing sample test is recommended according to age-appropriate activities for patients. In adults treated with blinatumomab, it has been found that a daily handwriting sample can often predict future nervous system toxicity before the clinical toxicity develops. In case of a change in finger-nose-finger or handwriting test it is recommended to start dexamethasone on the schedule above to prevent possible deterioration of nervous system toxicity. Patients who experience nervous system toxicity in the first cycle typically do not experience it again in subsequent cycles, although it is possible.

7.1 Management of Cytokine Release Syndrome (CRS), Neurologic Toxicity and Acute Graft Versus Host Disease During or Following Blinatumomab

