6.3.1 Source and Pharmacology

Blinatumomab is a fusion protein composed of two single-chain antibodies (scFv), murine anti-CD19 scFv and murine anti-CD3 scFv. Through CD3 binding, blinatumomab recruits and engages T cells for redirected lysis of CD19-positive B cells, including those expressed with B-cell malignancies. T cells are bound by its anti-CD3 moiety, whereas B cells are bound by the anti-CD19 moiety. The subsequent serial lysis of multiple malignant cells by a single blinatumomab-activated T cell closely resembles a natural cytotoxic T cell reaction. Treatment with blinatumomab is associated with a rapid depletion of peripheral B cells, accompanied by T cell activation and a transient increase in cytokines.

Blinatumomab consists of a single chain of 504 amino acids with a molecular weight of approximately 54 kDa. The pharmacokinetics of Blinatumomab was assessed over a dose range from 5 to 90 mcg/m²/day (approximately equivalent to 9-162 mcg/day). Following continuous intravenous infusion, the steady state serum concentration (Css) was achieved within a day and remained stable over time. The estimated mean (SD) volume of distribution based on terminal phase (V_z) was 4.52 (2.89) L. The estimated mean (SD) systemic clearance was 2.92 (2.83) L/hour and the estimated mean (SD) half-life was 2.11(1.42) hours. Negligible amounts of blinatumomab were excreted in the urine at the tested clinical doses. Like other protein therapeutics, blinatumomab is expected to be degraded into small peptides and amino acids via catabolic

pathways. At the clinical doses of 9 mcg/day and 28 mcg/day for the treatment of adult relapsed/refractory ALL, the mean (SD) Css was 211 (258) pg/mL and 621 (502) pg/mL, respectively.

Currently there are no known drug incompatibilities or interactions with blinatumomab.

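### Section 7.0 and Table 1 give different doses after a resolved interruption with no rule on which governs, and Table 1 is weaker than two mandatory stops in 7.0

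*Combined protocol and SAP*

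**What the plan says.** Section 7.0 of the combined protocol and SAP consists of prose, a NOTE and Table 1.

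- **Prose, same course.** If the event settles within 14 days, treatment may resume at 5 mcg/m²/day "to complete the 28-day course (not counting the duration of treatment interruption". No later dose step is described for that course.
- **Prose, next cycle.** After a related neurologic or psychiatric event of Grade 2 or worse, "no dose escalation beyond 5 mcg/m²/day will be permitted" in later cycles. For the rest: "For patients who experienced other AEs related to blinatumomab, subsequent cycles will begin at the reduced dose of 5 mcg/m²/day but" a step to 15 mcg/m²/day is allowed after 7 days.
- **Table 1, same course.** After Grade 3 cytokine release syndrome (CRS), neurologic toxicity or another relevant reaction, restart is at 9 mcg/day (45 kg and above) or 5 mcg/m²/day (below 45 kg). The heavier column then says "Escalate to 28 mcg/day after 7 days if the toxicity does not recur". The lighter column has the same step, to 15 mcg/m²/day. Table 1 is silent on the next cycle.
- **NOTE on stopping.** "For Grade 4 Nervous System/Psychiatric, Grade 3 or 4 Central Nervous System: Seizure and Grade 4 thromboembolic AEs, blinatumomab must be permanently discontinued".
- **Table 1 on stopping.** The seizure row reads "Discontinue blinatumomab permanently if more than one seizure occurs". The Grade 4 row for other reactions reads "Considering discontinuing blinatumomab permanently".
- **Pointers.** Sections 7.1.1 (CRS) and 7.1.2 (neurologic toxicity) refer staff to Table 1 for when to stop the infusion. Table 1 footnote 2 does so for neurologic events.

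**The concern.** Two instructions in one section lead to different doses for the same patient after the same toxicity, and nothing ranks them. A patient whose Grade 3 neurologic event has settled either stays at one third of the full dose for the rest of the course or is back at full dose a week after restart.

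Separately, the table that staff consult for stopping neurologic toxicity does not carry the full stopping rule. A reader of Table 1 could restart after a single Grade 3 seizure. A reader who looks up a Grade 4 thromboembolic event there finds advice to consider stopping, where the NOTE requires it.

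At stake is the safety and consistency of treatment in patients up to 25 years old at two sites. Section 7.0 itself names nervous system disorders and CRS as the most frequent serious events with this drug.

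**Working it through.** The plan gives no cumulative-dose figure to reproduce. The check is a side-by-side reading plus dose arithmetic.

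**Inputs.** Full dose is 15 mcg/m²/day below 45 kg and 28 mcg/day at 45 kg and above, for 28 days (Section 6.1). That is 15×28 = 420 mcg/m² or 28×28 = 784 mcg per cycle. Restart rules are those of Section 7.0 and Table 1. Section 6.3.1 gives the two dose scales as "from 5 to 90 mcg/m²/day (approximately equivalent to 9-162 mcg/day", which implies 9/5 = 1.8 m². The range 1.4 to 2.2 m² for patients of 45 kg and above is an assumption.

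**Starting dose at restart.** It is the same in both texts below 45 kg. At 45 kg and above it is 5×1.8 = 9 mcg/day against a fixed 9 mcg/day. The disagreement is about re-escalation.

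**Below 45 kg.** Let r be the infusion days left at restart, with no recurrence. Prose: 5r. Table 1: 5×min(r,7) + 15×max(r−7,0).

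| r | Prose (mcg/m²) | Table 1 (mcg/m²) | Prose / Table 1 |
|---|---|---|---|
| 25 | 125 | 305 | 41% |
| 21 | 105 | 245 | 43% |
| 14 | 70 | 140 | 50% |
| 10 | 50 | 80 | 63% |
| 8 | 40 | 50 | 80% |
| 7 | 35 | 35 | 100% |

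From day 8 after restart the daily ratio is 15/5 = 3. With r = 21, 7 full-dose days (7×15 = 105) came first. The course totals are 105+105 = 210 (50% of 420) and 105+245 = 350 (83%).

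**45 kg and above, r = 21.** Table 1: 7×9 + 14×28 = 455 mcg. Prose: 5×BSA×21 = 147, 189 or 231 mcg at 1.4, 1.8 or 2.2 m², which is 32%, 42% or 51% of Table 1. Daily ratio from day 8: 28/7 = 4.0, 28/9 = 3.1, 28/11 = 2.5.

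**Next cycle under the prose (per m²).** After a Grade 2 or worse neurologic or psychiatric event: 5×28 = 140 of 420 (33%). After other events: 7×5 + 21×15 = 350 of 420 (83%).

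**Stopping rules side by side.**

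| Event | Section 7.0 | Table 1 |
|---|---|---|
| First Grade 3 seizure | Permanent stop | Seizure row needs more than one; Grade 3 neurologic row allows restart |
| Grade 4 seizure | Permanent stop | Permanent stop (Grade 4 neurologic row) |
| Grade 4 thromboembolic | Permanent stop | Consider stopping (other reactions) |
| Second interrupting event, any type | Permanent stop | No rule |
| Grade 3 CRS unresolved at 14 days | Permanent stop | No time limit |
| Grade 3 neurologic, unresolved | Stop after 14 days | Stop after 7 days |
| Grade 4 CRS | Not in the NOTE | Permanent stop |

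Neither text is uniformly the stricter one.

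**The case against.** The strongest reply is that the two texts can be combined. The prose says only that treatment may resume, its explicit bar on escalation is limited to later cycles, and Table 1 can supply the missing step within the course. That reading is possible, but no sentence adopts it. It also gives an odd result: a patient with Grade 3 neurologic toxicity returns to full dose in Cycle 1 and is then held at one third of it throughout Cycle 2. The reply that Cycle 2 is limited to persistent MRD or donor delay is correct; it narrows the oddity without removing it.

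Some pointers do exist. Footnote 2 sends staff to Table 1 for interrupting or stopping, and to the prescribing information for psychiatric events that may reflect CNS toxicity. These are partial and do not settle re-escalation in general.

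On stopping, the objection has more force. Table 1 sits directly below the NOTE, and its seizure row does not expressly authorise restart after one Grade 3 seizure. A careful clinician can obey both texts by taking the stricter rule each time. That stands, but the protocol does not say to do so, and Section 7.1.2 and footnote 2 send neurologic cases to the weaker text.

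The 7-day and 14-day limits for Grade 3 neurologic toxicity might be read as a contradiction. They are not: stopping at 7 days satisfies both, so clarification is enough.

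**Conclusion.** The point holds. Re-escalation within an interrupted course is undetermined. The daily dose from day 8 after restart differs three-fold below 45 kg, and about 2.5- to 4-fold at 45 kg and above under the assumed 1.4 to 2.2 m². The course total with 21 infusion days left is 50% or 83% of plan below 45 kg. With 7 or fewer days left there is no difference below 45 kg. Table 1 is weaker than two explicit mandatory stops. The dose figures assume no recurrence after restart.

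Three stronger readings are not supported. A reader might infer that staff are told to rely on Table 1 alone. No text says so, and the pointers cover only CRS and neurologic toxicity; none sends thromboembolic events there. A reader might infer overdosing, but Table 1's higher branch never exceeds the protocol's standard dose. A reader might infer an effect on power, the response rate or the primary analysis set; nothing in the documents shows one, and none is claimed.

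The number of patients affected cannot be derived from the documents.

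**What to change.** 1. State in Section 7.0 one rule for restart dose and within-course re-escalation (for example, that Table 1 governs both). Delete or amend the conflicting sentence, and give one explicit Cycle 2 dose rule consistent with it. Which dose path is right is for the clinical team.
2. Keep the 14-day discontinuation limit for all interrupting events, with the 7-day limit for Grade 3 neurologic toxicity. Letting Table 1 govern time to resolution as well would remove the only limit for Grade 3 CRS. Keep the stop for a second interrupting event.
3. Change the Table 1 seizure row to: *Discontinue permanently for any Grade 3 or 4 seizure, or if more than one seizure occurs.*
4. Add to the Table 1 Grade 4 row for other reactions: *Discontinue permanently for Grade 4 thromboembolic AEs.*
5. State that where Section 7.0 and Table 1 differ on stopping, the stricter rule applies.

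The cost is one text-only amendment, with the IRB approval that Section 12.8 requires, and notice to both sites. Sample size, visits and assessments do not change.

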6.0 TREATMENT PLAN

6.1 Drug Administration

Up to 2 cycles of continuous infusion blinatumomab will be given based on the end of Cycle 1 disease response. Cycle 2 of blinatumomab can be given to subjects who have achieved remission (< 5% marrow blasts) after Cycle 1 but have persistent disease identified by multi-parameter flow cytometry (minimal residual disease (MRD) positive $\geq 0.01\%$) after Cycle 1. Additionally, subjects who achieved MRD negativity after Cycle 1 but are unable to proceed to HCT based on the timing/scheduling of the donor collection, a 2nd cycle of blinatumomab may be given. This additional cycle of blinatumomab for subjects awaiting donor collection, may be 28 days but can be less if the HCT is ready to proceed (e.g. 14-day blinatumomab infusion).

Minimal Organ Functions to be Met Before the Start of the Blinatumomab Infusion

Patients must meet the following criteria (prior to blinatumomab infusion)

- No oxygen requirement with oxygen saturations $> 90\%$.
- AST, ALT $< 5x$ upper limit of normal for age; bilirubin < 2 mg/dL.
- Hemoglobin > 8 mg/dL prior to infusion. (May be transfusion dependent).
- Renal function: serum creatinine $< 2 \times$ normal for age.
- Exhibit overt hematologic manifestations of relapse or persistent disease. Evidence of recurrent/persistent disease based primarily on flow cytometry, cytogenetics, chimerism analysis, or other molecular studies does not by itself represent grounds for exclusion.

Blinatumomab will be given as a 28-day continuous infusion with 14-days in between Cycle 1 and Cycle 2 as per the package insert and FDA approved labeling.

Cycle	Patient Weight Greater Than or Equal to 45kg (Fixed-dose)	Patient Weight Less Than 45kg (BSA-based dose)
1: Days 1-28	28 mcg/day	15 mcg/m ² /day (not to exceed 28 mcg/day)
Days 29-42	14-day treatment-free interval	14-day treatment-free interval
2: Days 1-28	28 mcg/day	15 mcg/m ² /day (not to exceed 28 mcg/day)
Days 29-42	14-day treatment-free interval	14-day treatment-free interval

Hospitalization is recommended for the first 3 days of Cycle 1 and the first 2 days of Cycle 2 (if needed).

Pre-medicate with prednisone or equivalent for MRD-positive B-cell Precursor ALL.

For patients \geq 18 years of age, pre-medicate with prednisone 100 mg intravenously or equivalent (e.g., dexamethasone 16 mg) 1 hour prior to the first dose of blinatumomab in each cycle.

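### Section 7.0 gives reduced Cycle 2 doses only per m², although subjects of 45 kg or more are fixed-dose, and its sentence on other related AEs states no grade or interruption condition

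*Combined protocol and SAP*

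**What the plan says.** Section 6.1 doses by weight. The upper band is headed "Patient Weight Greater Than or Equal to 45kg (Fixed-dose") and receives 28 mcg/day in both cycles. The band below 45 kg receives 15 mcg/m²/day, "not to exceed 28 mcg/day".

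Table 1 in Section 7.0 keeps this split when an infusion is withheld and restarted. Below 45 kg the doses are 5 then 15 mcg/m²/day. At 45 kg or more the restart is at 9 mcg/day, and then: "Escalate to 28 mcg/day after 7 days if the toxicity does not recur". The table's title limits it to events during administration, and it has no row for the next cycle.

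The text of Section 7.0 above the table covers the next cycle and has two rules:

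- After an event of at least "Grade 2 Neurologic Systems and Psychiatric AE related to blinatumomab", later cycles may not go above 5 mcg/m²/day.
- For everything else: "For patients who experienced other AEs related to blinatumomab, subsequent cycles will begin at the reduced dose of 5 mcg/m²/day but" with escalation to 15 mcg/m²/day permitted "after 7 days if there are no significant blinatumomab-related AEs".

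Neither rule has a weight band or repeats the 28 mcg/day cap. The resumption dose earlier in Section 7.0 is also given only as 5 mcg/m²/day. The opening rule of the section is narrower than the second bullet: it concerns "AEs related to blinatumomab that require treatment interruption (according to table below").

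**The concern.** There are two separate problems in one short paragraph.

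The first is the unit. Enrolment runs to age 25, so subjects of 45 kg or more are to be expected. Such a subject who had a related event in Cycle 1 and goes on to Cycle 2 has only one stated reduced dose, and it is on the scale that Section 6.1 and Table 1 reserve for lighter subjects. One study site may follow the paragraph as written and the other may carry Table 1's fixed doses forward, so the same Cycle 1 event can lead to different Cycle 2 doses.

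The second is the trigger. The other-AE sentence is mandatory but names no grade and does not say that the event must have interrupted treatment. Section 8.3 lists fever, headache and rash among the very common effects of the drug, so a literal trigger would be broad.

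What is at stake is correct dosing in Cycle 2. That is also the cycle in which subjects still MRD positive by flow cytometry after Cycle 1 can become responders on the primary endpoint.

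**Working it through.** **Inputs.** From the protocol: 28 mcg/day and 15 mcg/m²/day (Section 6.1); 9 then 28 mcg/day for 45 kg or more (Table 1); 5 then 15 mcg/m²/day for the next cycle (Section 7.0 text). The protocol gives no BSA for subjects of 45 kg or more, so 1.4, 1.8 and 2.0 m² are assumptions. Totals assume a full 28-day cycle with escalation on Day 8, that is 7 days at the lower dose and 21 at the higher.

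**Where the two scales agree.**

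- Reduced dose: 9 / 5 = 1.80 m².
- Full dose: 28 / 15 = 1.87 m².
- Section 6.3.1 equates 5 to 90 mcg/m²/day with about 9 to 162 mcg/day: 9 / 5 = 162 / 90 = 1.80 m², the same point.

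**Subjects of 45 kg or more, paragraph as written against Table 1's fixed doses.** Daily dose = mcg/m² × BSA. Total as written = (7 × 5 + 21 × 15) × BSA = 350 × BSA. Total by weight band = 7 × 9 + 21 × 28 = 651 mcg.

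| Assumed BSA | Start, against 9 mcg/day | Escalated, against 28 mcg/day | 28-day total, against 651 mcg |
|---|---|---|---|
| 1.4 m² | 7 (−22%) | 21 (−25%) | 490 (75%) |
| 1.8 m² | 9 (0%) | 27 (−4%) | 630 (97%) |
| 2.0 m² | 10 (+11%) | 30 (+7%) | 700 (108%) |

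The last row is the literal text. If the 28 mcg/day full dose is respected on escalation, it becomes 7 × 10 + 21 × 28 = 658 mcg, and 658 / 651 = 101%.

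**Neurologic ceiling over 28 days, 45 kg or more.** As written, 28 × 5 × BSA = 196 / 252 / 280 mcg at 1.4 / 1.8 / 2.0 m². At a 9 mcg/day ceiling, 28 × 9 = 252 mcg. The ratios are 78% / 100% / 111%.

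**Cost of the literal trigger.** These figures apply only if the other-AE sentence is read without an interruption condition.

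- Below 45 kg: planned 28 × 15 = 420 mcg/m². With a reduced start, 350 mcg/m² (83%). Never escalated, 28 × 5 = 140 mcg/m² (33%).
- 45 kg or more, by weight band: planned 28 × 28 = 784 mcg. With a reduced start, 651 mcg (83%). Never escalated, 252 mcg (32%).

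**Evidence on the intended trigger.** The opening rule of Section 7.0 concerns related events that require interruption. The resumption rule that follows sets a reduced dose after such an event, and the other-AE sentence refers back to that reduced dose. The next rule concerns a second event requiring interruption, which presupposes a first of that kind. All of this points to interruption. On the other side, the neurologic ceiling starts at Grade 2, whereas Table 1 withholds for graded neurologic toxicity only from Grade 3. So the paragraph is not tied to interruption throughout.

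**The case against.** The strongest reply is that the equivalence is easy to find. Table 1 sets 9 mcg/day beside 5 mcg/m²/day and 28 beside 15, and Section 6.3.1 gives the same 5-to-9 conversion. A careful pharmacist would probably use the fixed doses. This lowers the practical risk. It does not remove the defect, because Table 1 covers restarts within a cycle and the next-cycle text states a different figure.

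It can also be said that an escalation back to full dose cannot sensibly exceed the full dose. That stands: the 30 mcg/day figure is what the words give, not a likely practice, and with the cap the excess at 2.0 m² is about 1% of the total.

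Four stronger readings might be inferred, and the documents do not support them:

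- *An escape from the neurologic stop rule.* For 45 kg or more Table 1 says: "If the toxicity occurred at 9 mcg/day, or if the toxicity takes more than 7 days to resolve, discontinue blinatumomab permanently". A 1.4 m² subject held at 5 mcg/m²/day is on 7 mcg/day, so it might seem that the rule is missed and the infusion restarts at 9. But the same ceiling bars any dose above 5 mcg/m²/day, and Section 7.0 stops treatment permanently at a second event requiring interruption.
- *Mostly under-dosing, in most heavier subjects.* This needs a BSA distribution, and the protocol gives none. The error runs in both directions.
- *The trigger is invisible in the trial data.* Section 8.4 does exempt Grade 1 and 2 events from reporting. But Section 5.2.1 has adverse events evaluated weekly, so the treating team would know of them, and Section 10.7.6 makes cytokine release syndrome and neurological events reportable with no grade limit.
- *The missing condition is a proven dosing error.* The surrounding text leans towards interruption but is not uniform, so this is an ambiguity.

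**Conclusion.** The unit defect holds on the text. For subjects of 45 kg or more, the only stated reduced next-cycle dose is on the wrong scale and lacks the cap. It matches the protocol's fixed doses only at 1.80 m² (reduced) and 1.87 m² (full). Over the assumed range of 1.4 to 2.0 m², the 28-day total runs from 75% to 108% of the weight-banded total, or to 101% if 28 mcg/day is respected.

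The missing condition holds as an ambiguity in a mandatory sentence. The intended trigger is an inference that only the sponsor can confirm.

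The reach is narrow: subjects who receive Cycle 2 after a related Cycle 1 event, and for the units only those of 45 kg or more, within a maximum of 35 enrolled. How many that is, and any effect on the response rate, cannot be worked out from the documents. No sample size, error rate or power figure changes. It is a dosing-clarity defect, worth correcting because the instruction governs dosing and the correction is cheap.

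**What to change.** Amend Section 7.0 to state the resumption dose, the next-cycle doses and the neurologic ceiling by the protocol's own weight bands:

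| Weight | Resumption or next-cycle start | After escalation, where allowed | Ceiling after a related neurologic or psychiatric event of Grade 2 or higher |
|---|---|---|---|
| 45 kg or more | 9 mcg/day | 28 mcg/day | 9 mcg/day |
| Below 45 kg | 5 mcg/m²/day | 15 mcg/m²/day, capped at 28 mcg/day | 5 mcg/m²/day |

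The Grade 2 neurologic threshold can stay as a conservative choice; only its unit needs correcting.

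Have the sponsor confirm the intended trigger of the other-AE sentence. If it is what the surrounding text suggests, limit the sentence to related events that required interruption under Table 1. Add a cross-reference to the next-cycle rule in Table 1 and beside the Section 6.1 dose table.

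The cost is amendment wording only, with no extra patients, visits or procedures.
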